Adverse events ^b		Continuous from ICF through 30 days (or 90 days for SAEs) after the last dose of study drug or start of subsequent anticancer therapy, if earlier (see Section 12.3.1)									
Prior and Concomitant Medications		Continuous 30 days prior to 1st administration of study drug through 30 days after last dose of study drug									
Survival and subsequent anti-cancer therapy											X

AE=adverse event, C=cycle, CRF=case report form, COPD=chronic obstructive pulmonary disease, CT=computed tomography, D or d=day, ECOG= Eastern Cooperative Oncology Group Performance Status, EOT=end of treatment, FEV-1=forced expiratory volume; maximal amount of air forcefully exhaled in 1 sec., HBV=hepatitis B virus, HCV=hepatitis C virus, IAT=indirect antiglobulin test, ICF=informed consent form, MRI=magnetic resonance imaging, PD=progressive disease, PD-L1=programmed death-ligand 1, Ph=phase, q=every, SIPPM=Site Investigational Product Procedures Manual

- Safety Run-in and Arm B only:** C1D1: measure vital signs immediately before the start of the infusion; at 0.5, 1, 1.5, 2 and 3.5 hrs after the start of the infusion; at the end of the infusion; and 0.5 and 1 hr after the end of the infusion. For all subsequent Safety Run-in and Arm B administrations (daratumumab + atezolizumab), measure immediately before the administration start, at the end of the atezolizumab infusion, and as clinically indicated. **Arm A only:** vital signs should be assessed at Screening, within 24 hrs of the start of each infusion and at the end of each infusion.
- Beginning with the implementation of Amendment 7, only serious adverse events will be reported and entered in the Sponsor safety repository for subjects who continue to be treated according to local regulatory approval and standard of care guidelines.^{50,51}

ABBREVIATIONS

ADCC	antibody dependent cell-mediated cytotoxicity
AE	adverse event
ALK	anaplastic lymphoma kinase
Breg	regulatory B cell
CBC	complete blood count
CBR	clinical benefit rate
CDC	complement-dependent cytotoxicity
COPD	chronic obstructive pulmonary disease
CR, sCR	complete response; stringent complete response
CRF	case report form(s) (paper or electronic as appropriate for this study)
CT	computed tomography
CyTOF	cytometry time of flight
DCF	data clarification form
DLT	dose-limiting toxicity
DMC	Data Monitoring Committee
DoR	duration of response
ECG	electrocardiogram
ECOG	Eastern Cooperative Oncology Group Performance Status

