11.8. Safety Analyses

Adverse Events

The verbatim terms used in the CRF by investigators to identify adverse events will be coded using the Medical Dictionary for Regulatory Activities (MedDRA). Treatment-emergent adverse events are AEs with onset during the treatment phase or that are a consequence of a pre-existing condition that has worsened since baseline. All reported adverse events will be included in the analysis. For each adverse event, the percentage of subjects who experience at least 1 occurrence of the given event will be summarized by treatment group. In addition, comparisons between treatment groups will be provided if appropriate.

Summaries, listings, datasets, or subject narratives may be provided, as appropriate, for those subjects who die, who discontinue treatment due to an adverse event, or who experience a severe or a serious adverse event.

Clinical Laboratory Tests

Laboratory data will be summarized by type of laboratory test. Reference ranges and markedly abnormal results (specified in the Statistical Analysis Plan) will be used in the summary of laboratory data. Descriptive statistics will be calculated for each laboratory analyte at baseline and for observed values and changes from baseline at each scheduled timepoint. Changes from baseline results will be presented in pre- versus posttreatment cross-tabulations (with classes for below, within, and above normal ranges). A listing of subjects with any laboratory results outside the reference ranges will be provided. A listing of subjects with any markedly abnormal laboratory results will also be provided.

Parameters with predefined NCI-CTCAE toxicity grades will be summarized. Change from baseline to the worst adverse event grade experienced by the subject during the study will be provided as shift tables.

Electrocardiogram

Electrocardiogram data will be summarized based on categories of normal, abnormal either clinically significant or not clinically significant and listed.

Vital Signs

Descriptive statistics of temperature, pulse/heart rate, and blood pressure (systolic and diastolic) values and changes from baseline will be summarized at each scheduled timepoint. The percentage of subjects with values beyond clinically important limits will be summarized.

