12.3. Procedures

12.3.1. All Adverse Events

All adverse events and special reporting situations will be reported from the time a signed and dated ICF is obtained until 30 days after the last dose of study drug (or 90 days for serious adverse events), or until start of subsequent anticancer therapy or the subject withdraws consent

for study participation, if earlier, which may include contact for follow-up of safety. For subjects who have received subsequent treatment with therapeutic intent for NSCLC during the adverse event reporting period, only adverse events that are considered to be possibly, probably, or definitely related to atezolizumab or daratumumab need to be reported. Serious adverse events, including those spontaneously reported to the investigator, must be reported using the Serious Adverse Event Form. The Sponsor will evaluate any safety information that is spontaneously reported by an investigator beyond the time frame specified in the protocol.

Disease progression should not be recorded as an adverse event or serious adverse event term; instead, signs and symptoms of clinical sequelae resulting from disease progression/lack of efficacy will be reported if they fulfill the serious adverse event definition (refer to Section 12.1.1). Death should not be recorded as an adverse event or serious adverse event, but as the outcome of an adverse event. The adverse event that resulted in the death should be reported as a serious adverse event. All events that meet the definition of a serious adverse event will be reported as serious adverse events, regardless of whether they are protocol-specific assessments. Anticipated events will be recorded and reported as described in [Attachment 4](#).

All adverse events, regardless of seriousness, severity, or presumed relationship to study drug, must be recorded using medical terminology in the source document and the CRF. Whenever possible, diagnoses should be given when signs and symptoms are due to a common etiology (eg, cough, runny nose, sneezing, sore throat, and head congestion should be reported as "upper respiratory infection"). Investigators must record in the CRF their opinion concerning the relationship of the adverse event to study therapy. All measures required for adverse event management must be recorded in the source document and reported according to Sponsor instructions.

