12.4. Safety Reporting for Atezolizumab Monotherapy Subjects (per Amendment 6)

Following implementation of Amendment 6, all adverse events and special reporting situations (with the exception of Grade 1 to 2 events and non-immune-mediated events) will be reported from the time a signed and dated ICF is obtained until 30 days after the last dose of study drug (or 90 days for serious adverse events), or until withdrawal of consent for study participation. For subjects who have received subsequent treatment with therapeutic intent for NSCLC during the adverse event reporting period, only adverse events that are considered to be possibly, probably, or definitely related to atezolizumab need to be reported; all other Grade 1 to 2 AEs, including laboratory abnormalities, do not need to be recorded in the CRF, but should be recorded in the source documentation.

Beyond 90 days after the last dose of study drug, SAEs, considered possibly, probably, or definitely related to study drug will continue to be collected and reported into the Sponsor's global safety database, using the SAE Form (paper form) faxed to Sponsor's Local Operational Company/Local Safety Officer. These should be reported until the subject discontinues the study (per the definitions in Section 10.2). SAEs (see Section 12.3.2) should include information on study agent administration and concomitant medications and other treatments associated with the SAE.

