2.6.9. Relationship of Adverse Events to Study Medication

For each adverse event, its relationship to study medication is determined by investigator and recorded on the eCRF. An adverse event is considered as related to study medication if the relationship is possible, probable or very likely.

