2.6.10. Treatment Emergent Adverse Events

Treatment emergent adverse events (TEAEs) are defined as any AE with onset date and time on or after that of the first dose through 30 days after the last study drug administration, or the day prior to start of subsequent therapy, whichever is earlier; or any AE that is considered related to (very likely, probably, or possibly related) study medication regardless of the start date of the event. AEs with missing or partial onset date and time will be considered as treatment-emergent unless the onset date and time of an AE can be determined as earlier than that of the first dose, or later than 30 days after last study drug administration.

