6.1. Adverse Events

Unless otherwise specified, only TEAEs will be summarized.

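### Serious adverse events are collected to 90 days after last dose, but the SAP's adverse event outputs omit those starting on days 31-90 unless the open-label investigator rates them related

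*SAP*

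**What the plan says.** **Collection.** Protocol Section 12.3.1 has events reported "until 30 days after the last dose of study drug (or 90 days for serious adverse events"), ending earlier if the subject starts subsequent anti-cancer therapy or withdraws consent. The adverse event row of Protocol Table 1 agrees: "Continuous from ICF through 30 days (or 90 days for SAEs) after the last dose of study drug". Section 12.4, added by Amendment 6, keeps the longer period for serious events: "or 90 days for serious adverse events), or until withdrawal of consent for study participation".

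**Analysis commitment in the protocol.** Section 11.8 states: "All reported adverse events will be included in the analysis". Its own definition of treatment-emergent refers to onset in the treatment phase or worsening from baseline, and gives no number of days.

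**Analysis rule in the SAP.** Section 6.1 states: "Unless otherwise specified, only TEAEs will be summarized". Section 2.6.10 defines a treatment-emergent adverse event (TEAE) as one with onset from first dose "through 30 days after the last study drug administration", or up to the day before subsequent therapy if that comes first. A second route admits any event considered related to "study medication regardless of the start date of the event". Under Section 2.6.9, for each event "its relationship to study medication is determined by investigator and recorded on the eCRF"; possible, probable and very likely count as related. In Section 6.1.1 all the serious-event tables are tables of serious TEAEs, and the listing is a listing of TEAEs.

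**Deaths.** SAP Section 6.2 summarises and lists every death during the study, with its primary cause and no day limit. It adds a separate summary of deaths within 30 days of the last infusion. SAP Section 5.3.4 analyses overall survival from randomization with death from any cause as the event.

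**The concern.** The protocol sets a longer collection period for serious events than for other events, but the SAP gives them no longer analysis period. After day 30, an SAE reaches the adverse event tables only through an attribution made by an investigator who knows the treatment arm. The same late event could be rated differently in a subject on an untested combination and in a subject on a familiar monotherapy. That could distort the between-arm comparison in either direction.

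Post-treatment serious events also matter in this trial. Protocol Section 1.4 reports that the Data Monitoring Committee saw no unexpected imbalance in on-treatment toxicities but did note numerically more deaths in the combination arm. A reader of the study report will want to see what serious events occurred after treatment stopped, by arm. The SAP does not fully provide this, although the data are collected.

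**Working it through.** No power or error-rate figure is involved. The check is window arithmetic and a trace of where a late SAE would appear.

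**Step 1: the windows.**
- SAE collection after last dose: 90 days (Protocol Table 1; Protocol Section 12.3.1).
- TEAE onset window after last dose: 30 days (SAP Section 2.6.10).
- Uncovered period: 90 - 30 = 60 days, and 60 / 90 = 67% of post-dose SAE collection.

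This is a maximum. If subsequent therapy starts on day *s* after the last dose, with *s* between 31 and 90, the uncovered period is about *s* - 30 days. If it starts by day 30, nothing collected as unrelated is lost to the 30-day cut, because collection has already narrowed. From that point Protocol Section 12.3.1 requires only related events to be reported.

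**Step 2: where an SAE with known onset on days 31-90 appears**, for a subject with no subsequent therapy:

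| | Rated possible, probable or very likely | Rated not related or doubtful |
|---|---|---|
| Non-fatal | Serious TEAE tables and TEAE listing | No adverse event table or listing |
| Fatal | Serious TEAE tables, death-due-to-TEAE tables, deaths summary and listing, overall survival | Deaths summary and listing (with cause) and overall survival only |

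The right-hand column is the gap. In its lower cell the death is not lost, but the adverse event behind it is missing from the adverse event outputs. Protocol Section 12.3.1 requires that event to be reported as an SAE.

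**Step 3: does another SAP rule bring these events back?**
- Events with a missing or partial onset date default to treatment-emergent unless they can be placed before first dose or beyond 30 days after the last (SAP Section 2.6.10). This recovers some events, but none with a complete onset date on days 31-90.
- The sections on infusion-related reactions and immune-mediated events (SAP 6.1.2.1 and 6.1.2.3) set no longer window.
- Protocol Section 11.8 allows summaries, listings or narratives for serious events, but only as an option, and the SAP specifies none beyond TEAEs.

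**Step 4: which collection rule applies to the report.** Protocol Sections 3.2 and 17.9.1 base the clinical study report on the data reviewed on 23 May 2018. Amendment 6 is dated 14 August 2018, so those data were collected under the earlier reporting rules. The 90-day SAE period is in any case unchanged in Section 12.4.

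**The case against.** The opposing case has several parts, and much of it stands.

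- **Deaths.** A reader might infer that late deaths are hidden, or that the mortality comparison passes through unblinded attribution. The documents do not support this. SAP Sections 6.2 and 5.3.4 count deaths whatever their cause, timing or attribution, and the Data Monitoring Committee was able to note the imbalance.
- **Delayed immune events.** A reader might infer that these are the main loss. That is unlikely. Both arms receive atezolizumab, and a late event flagged as immune-mediated would ordinarily be rated at least possible, so it would enter through the related clause, which has no time limit. SAP Section 6.1.2.3 also promises a listing of all immune-mediated events, which can be read as not limited to TEAEs.
- **Contradiction with the protocol's TEAE definition.** There is none. That definition has no day limit, and the follow-up phase begins after the end-of-treatment visit, about 30 days after the last dose. A 30-day TEAE window is compatible with it. The conflict rests on the Section 11.8 commitment to all reported events, together with the 90-day collection rule. Section 11 describes itself as general and leaves detail to the SAP, which softens the conflict, but leaving out events already collected goes beyond adding detail.
- **Disease-related events.** Sequelae of progression that meet the serious criteria are reportable, so some late unrelated SAEs will reflect the cancer. This is a good reason to keep them out of the TEAE tables. It does not justify omitting them from all adverse event outputs.

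**Conclusion.** The point holds in a limited form. For subjects who start no subsequent therapy by day 90, up to 60 of the 90 days of post-dose SAE collection lie outside the SAP's onset window. In that period, non-fatal SAEs rated unrelated or doubtful have no specified table or listing, and fatal ones lose their event-level record in the adverse event tables. The filter is the judgment of an investigator who knows the arm.

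The conclusion assumes a known onset date and reads the SAP's list of outputs as complete. The number of events affected is not given, and neither the presence nor the direction of bias can be shown from the documents. This is an incomplete safety report against the protocol's own commitment. It is not evidence that mortality or immune toxicity is misreported.

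**What to change.** In SAP Sections 2.6.10 and 6.1.1:

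1. Keep the 30-day TEAE definition and the existing TEAE tables.
2. Add a by-arm table, by system organ class and preferred term, and a listing of all SAEs with onset from first dose to 90 days after last dose, or to the day before subsequent anti-cancer therapy if earlier, regardless of attribution.
3. For Arm A subjects who crossed over, show events after crossover separately, so that they are not counted against monotherapy.

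Do not extend the window for non-serious immune-mediated events. They are collected only to 30 days, so there would be no systematic data to fill it. A count of deaths within 90 days beside the 30-day count is optional, since all deaths are already reported.

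The cost is one window flag and a few outputs from data already collected. The minor downside is that some disease-related events will be added in both arms; a footnote can say so.

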3. INTERIM ANALYSIS AND DATA MONITORING COMMITTEE REVIEW

An internal Janssen DMC, independent of the study team, will be established to review the efficacy and safety data in the randomization phase. The DMC will consist of a minimum of 3 members with at least 1 clinician and a statistician, 1 of whom will chair the committee. The DMC will review the totality of data after approximately 40, 60, and 90 subjects have been enrolled, and will formulate recommendations on study conduct (see protocol Section 11.3). The DMC may request additional ad-hoc reviews as data accumulate.

Additional details will be specified in a separate DMC charter.

4. SUBJECT INFORMATION

4.1. Demographics and Baseline Disease Characteristics

Subject eligibility will be summarized for all subjects with a non-missing informed consent date. Number of subjects who did not meet all inclusion/exclusion criteria will be summarized, together with the specific non-met criterion. A listing of subjects who didn't meet all inclusion/exclusion criteria will be provided.

Subject enrollment will be summarized by country and site.

The following baseline demographic and disease characteristics will be summarized:

- Demographics: age (continuous), age category (< 65 years and ≥ 65 years), sex (male, female), race (white, non-white, unknown, and not reported), ethnicity (Hispanic, Non-Hispanic, unknown, and not reported), height (cm), weight (kg), and ECOG performance status score (0, 1).

- Baseline disease characteristics: Tumor stage at initial diagnosis and study entry (0, I, II, III, IV, not applicable, unknown), time since initial diagnosis (years), and diagnosis subtype (squamous, non-squamous).

In addition, baseline laboratory tests will be summarized, as appropriate. The frequencies of CTC toxicity grade for these laboratory parameters at baseline will be provided, if applicable.

General medical history will be summarized by body system and condition status as reported on eCRF. A listing will be generated for abnormal medical history.

A listing for procedures performed after date of informed consent will be provided.

Vital signs, including body temperature, pulse, systolic blood pressure and diastolic blood pressure at baseline will be summarized.

ECG results at baseline will be summarized by overall interpretation: normal, abnormal and clinically significant, abnormal and not clinically significant, and other.

Spirometry measurement of percent predicted FEV1 will be summarized, if applicable.

Categorical summary of the stratification factors will be also be presented.

4.2. Disposition Information

Number of subjects who discontinued from treatment will be summarized, together with reason reported on eCRF. Number of subjects who discontinued from study and the reported reason on eCRF will be presented similarly. A listing for subject disposition will also be provided.

4.3. Treatment Compliance

Refer to section 4.4.

4.4. Extent of Exposure

Duration of treatment in months will be summarized, together with the number of treatment cycles. Descriptive statistics for the total dose received, total number of infusions, and relative dose intensity (%) will be provided for Daratumumab and Atezolizumab, respectively.

The frequencies of actions planned prior to infusion start and taken during infusion will be summarized, together with reasons reported on eCRF.

For cross-over subjects, exposure data after initiation of cross-over treatment may be summarized separately, as applicable.

4.5. Protocol Deviations

The incidence of major protocol deviation, together with the corresponding deviation terms will be summarized. A listing of all major protocol deviations will be provided.

4.6. Prior and Concomitant Medications

The number of lines of prior systemic therapy will be summarized descriptively as well as by the following categories: 1 and > 1. Frequency will also be presented for subjects selected types of prior therapies. A listing will be provided for prior cancer-related surgery or radiotherapy.

Use of concomitant therapies will be provided by therapeutic class, pharmacologic class, and preferred term.

Pre-infusion medications will be grouped by analgesics, antihistamines, and corticosteroids (intermediate and long-acting). The incidence of pre-infusion medications will be presented by the aforementioned groups and preferred terms. The same summary will be provided for post-infusion medications.

4.7. Subsequent Anti-cancer Treatments

Subsequent anti-cancer treatments, including radiotherapy, surgery, and systemic therapy, will be summarized.

5. EFFICACY

5.1. Analysis Specifications

5.1.1. Level of Significance

All 95% confidence intervals presented will be 2-sided.

5.1.2. Data Handling Rules

There is no imputation planned for missing efficacy endpoint values.

For cross-over subjects, efficacy data after initiation of cross-over treatment may be summarized separately, as applicable.

5.2. Primary Efficacy Endpoint

The primary efficacy endpoint is overall response rate (ORR).

Definition

The primary endpoint is overall response rate (ORR), defined as the proportion of subjects who achieve a response of partial response (PR) or better.

Analysis Methods

Analysis will be based on the ITT population, and response evaluable population. The number and percentage of subjects along with two-sided 95% exact confidence interval (CI) will be provided by treatment group in the following response categories: CR, PR, ORR, stable disease (SD), clinical benefit rate (CBR), progressive disease (PD), and not evaluable (NE).

Odds ratio of achieving response for Arm B over Arm A and its 95% confidence interval will be provided.

ORR will also be presented by the subgroups specified in Section 2.4, as appropriate.

